Appendix 5: PrEP Screening for Substantial Risk and Eligibility (ICAP)

Pre-Exposure Prophylaxis (PrEP) Screening for Substantial Risk and Eligibility

1. Facility Information		
Facility Name		
Date of Initial Client Visit (dd/mm/yyyy) ____ / ____ / ____	Person Completing Form	
/ ____ / ____		
2. Client Information		
First Name	Middle Name	Surname
Address	Telephone #	

Client ID Number

3. Client Demographics

What was your sex at birth?	 Male  Female  No response	 Other (specify): _____
What is your current gender?	 Male  Female  Transgender (male to female)  Transgender (female to male)  Other (specify): _____	 Transgender
What is your age? (Specify number of years.)	_____	

4. Screening for Substantial Risk for HIV Infection

Client is at substantial risk if he/she belongs to categories ①, ②, or ③ below	Question Prompts for Providers
① If client is sexually active in a high HIV prevalence population PLUS reports ANY one of the below in the last 6 months	Have you been sexually active in the last 6 months?
 Reports vaginal or anal intercourse without condoms with more than one partner	In the last 6 months, how many people did you have vaginal or anal sex with? In the last 6 months, did you use condoms consistently during sex?
 Has a sex partner with one or more HIV risk:	In the last 6 months, have you had a sex partner who: 
 • Is living with HIV? • Injects drugs? • Has sex with men? • Is a transgender person? • Is a sex worker? • Has sex with multiple partners without condoms?

 History of a sexually transmitted infection (STI) based on self-report, lab test, syndromic STI treatment	In the last 6 months, have you had an STI?
 History of use of post-exposure prophylaxis (PEP)	In the last 6 months, have you taken post-exposure prophylaxis (PEP) following a potential exposure to HIV?
② If client reports history of sharing injection material or equipment in the last 6 months  History of sharing injection material or equipment	In the last 6 months, have you shared injecting material with other people?
③ If client reports having a sexual partner in the last 6 months who is HIV positive AND who has not been on effective* HIV treatment (i.e., the partner has been on ART for fewer than 6 months or has inconsistent or unknown adherence)  History of HIV-positive sex partner not on effective treatment	Is your partner HIV positive? Is he/she on ART? What was the last viral load result?

5. PrEP Eligibility

Client is eligible if he/she fulfills ALL the criteria below:	
 HIV negative	Date client tested: (dd/mm/yyyy): ____ / ____ / _____ Date client received test results: (dd/mm/yyyy): ____ / ____ / _____ Test result:  Negative  Positive (Refer to HIV medical care.)  Inconclusive (Re-test in 14 days.)

Type of test used:  Determine  Unigold  ELISA  Other (specify): _____	
 At substantial risk of HIV	At least one item/risk in Section #4 above is ticked
 Has no signs/symptoms of acute HIV infection	See Section #6 below to confirm no recent exposure to HIV
 Has creatinine clearance (eGFR) >60 ml/min	Result: _____ Date of creatinine test (dd/mm/yyyy): ____ / ____ / _____
If all boxes in Section 5 are ticked, offer PrEP.	

6. Recent Exposure to HIV

Ask the client:

In the past 72 hours, have you had sex without a condom with someone whose HIV status is positive or not known to you, or have you shared injection equipment with someone whose HIV status is positive or unknown to you?

In the past 28 days, have you had symptoms of a cold or flu, including fever, fatigue, sore throat, headache, or muscle pain or soreness?

 Yes* <small>*</small>	 No	 Don't know
	 No	 Don't know

* If the client reports potential exposure to HIV within past 72 hours, do NOT offer PrEP.

Follow facility procedures to evaluate further or refer for evaluation for post-exposure prophylaxis (PEP).

** If the client reports flu-like symptoms or other signs of acute HIV infection, do NOT offer PrEP and evaluate further, following facility procedures to diagnosis acute HIV infection.

7. Services Received by Client

 PrEP offered.

 •  PrEP accepted. •  PrEP declined. (If declined, see Reasons for Declining PrEP, below).

Date eligible (dd/mm/yyyy): ____ / ____ / _____

Date initiated (dd/mm/yyyy): ____ / ____ / _____ *Same-day initiation recommended.*

Reasons for Declining PrEP

(Check all that apply.)

- No need for PrEP
 - Does not wish to take a daily medication
 - Concerns about side effects
 - Concerns about what others might think
 - Concerns about time required for clinic follow-up
 - Concerns about safety of medication
 - Concerns about effectiveness of medication
 - Other (specify):
-
- Referred for PEP evaluation
 - Referred for PCR/HIV Ag test or follow-up HIV re-testing (if suspicion of acute HIV infection)

Appendix 6: VSQ-9

Patient Satisfaction Survey

Thinking about your visit with the physician/health care Professional you saw, how would you rate the following:

	Poor	Fair	Good	Very Good	Excellent
1. How long you waited to get an appointment					
2. Convenience of the location of the office					
3. Getting through to the office by phone					
4. Length of time waiting at the office					
5. Time spent with the physician/health care professional you saw					
6. Explanation of what was done for you					
7. Technical skills (thoroughness, carefulness, competence) of the physician/health care professional you saw					
8. The personal manner (courtesy, respect, sensitivity, friendliness) of the person you saw					
9. The visit overall					

Appendix 7: GRIP

Excellent	Very Good	Good	Fair	Poor	Very Poor
Identify/remind patient about available adherence support resources	Offer opportunity to use/participate in 1 or more available adherence support interventions	Recommend use of/participation in 1 or more available adherence support interventions	Strongly recommend use of/participation in 1 or more available adherence support interventions		

Appendix 8: Treatment Facility Survey

Treatment Facility Survey (ETF)

Date of assessment:

1. What type of provider/program is this?
 - a. Office based provider
 - b. Substance use treatment program
 - c. Inpatient facility
 - d. Other:

2. Was this patient engaged in a program at your facility or being treated at your office for their alcohol use disorder?

If "Yes", please review and answer the following questions.

3. What was the date of their admission into your program, or if office-based, when did their care begin?
4. Indicate the type(s) of treatment they are receiving for their alcohol use disorder:

- a. Naltrexone treatment:

- i. Oral:

- ii. Injectable:

- b. Short-term detoxification

- c. Inpatient

- d. Other:

5. How would you categorize the level of treatment received by this patient?

- a. No care received

- b. Level 1: Outpatient treatment

- c. Level 2: Intensive outpatient treatment (including partial hospitalization)

- d. Level 3: Clinically managed residential/inpatient treatment

- e. Level 4: Medically managed intensive inpatient treatment

- f. Other:

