Laboratory abnormalities will be addressed using standard ED clinical protocols. Patient with critical values will be asked to return to the ED for repeat evaluation and laboratory testing. Patients with abnormal values (HBV+ or elevated eCrCl) will be referred for out-patient evaluation. If a patient is found to have a clinical contraindication for PrEP their study participation will end.

Enrolled participants will also be asked to complete a number of validated and study team developed measures including:

- 1) Locator form with additional demographics (Appendix 1)
- 2) Satisfaction questionnaire and qualitative assessment (Appendix 2).
- 3) Attitudes towards PrEP Scale (Appendix 3)
- 4) CDC Sexual Behavior Questions (CSBQ) (Appendix 4)

to ED discharge all patients will receive a referral to an out-patient PrEP provider. Referrals are made through the Institute of Advanced Medicine (IAM) PrEP Warm Line, the IAM REDCap referral system, or via [contact]. Patients will also be asked to sign an Authorization for Release of Medical

Information. The medical release form is needed to confirm clinic follow-up for patients not receiving their follow-up care within the Mount Sinai Health System.

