9.5 Follow-up

All follow-up assessments will be performed over the phone. Follow-up assessments will occur at 30, 60, and 90 days post enrollment.

Follow-up assessments will include:

- 1) Attitudes toward Pre-Exposure Prophylaxis Scale (APS) (Appendix 3)
- 2) Section 4 of ICAP "Screening for Substantial Risk of HIV" (Appendix 5)
- 3) Satisfaction questionnaire and qualitative assessment and visit specific satisfaction instrument (VSQ-9) (Appendix 6)
- 4) Adherence information measured by (1) self-report. Self-report will be assessed with the single measure Guidelines Regimen Information Program (GRIP) guide and questions on last dose and number of missed doses since prior follow-up. (Appendix 7)
- 5) CDC Sexual Behavior Questions (CSBQ) (Appendix 4)
- 6) STAR*D PRISE (Side-effect assessment)

Assessment of engagement in PrEP care at 30, 60, and 90 days post enrollment will be verified by direct contact with the treatment provider/program provided or by EMR review if the patient is linked within the Mount Sinai Health System. If the patient is receiving their PrEP care outside of the Mount Sinai Health System, a signed release authorization form will be sent.

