10.5 Outcome Data

10.5.1 Engagement in Treatment Survey (Primary Outcome)

At 30, 60, and 90 days post enrollment, participants will be asked to report PrEP use and engagement in PrEP care. The services reported by the patient will be confirmed with the treatment provider or by review of the patient's medical record.

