10.5.2 Treatment Facility Survey (Appendix 8)

The treatment facility survey will be completed to confirm where the patient is receiving PrEP follow up care. If they are outside of Mount Sinai Health System, they will be sent a signed authorized release form (Appendix 9).

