11.1.3 Sample Size

pilot RCT will be insufficiently powered to provide definitive efficacy data on retention and adherence for two study arms at 90 days. Yet, the pilot data is needed to determine recruitment and attrition rates, as well as means and standard deviations for key measures that will be needed to plan a definitive trial of ED-initiated

PrEP. For illustrative purposes we have included the following table of powers based on different retention in care rates in the control and experimental groups with the assumption that those retained in care will be using PrEP. This analysis assumes initial groups sizes of 40 and 40. The test statistic used is the two-sided Z test with pooled variance. The significance level of the test was targeted at 0.0500.

Power	Control Group	Experimental (iPrEP) Group	Difference in Proportions
	Retained in Care/PrEP	Retained in Care/PrEP	
0.0812	50%	55%	5%
0.1571	50%	60%	10%
0.2859	50%	65%	15%
0.4581	50%	70%	20%
0.6474	50%	75%	20%
0.8166	50%	80%	30%
0.9327	50%	85%	35%

The 50% follow-up rate for the control arm is based on and manuscript by Bogoch et als. entitled “Attrition Between the Emergency Department and Clinic Among Individuals Presenting for HIV Non-occupational Post exposure Prophylaxis published in *Clinical Infectious Diseases* in 2014.⁷⁴ The authors found that only 54% of patients seen in the ED for non-occupational post-exposure prophylaxis attended their first follow-up post-exposure clinic visit. This study did use appointment reminders but not the degree of facilitated linkage that will be used for the described ED PrEP program. In Project BRIEF, the HIV testing program described in the preliminary studies, the follow-up rate for newly infected HIV patients was 85%. Given that this will be the first effort at PrEP screening, initiation and linkage in the Emergency Department we do not expect to achieve the same degree of retention in care as we did for follow-up in Project BRIEF.

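### The Treatment Facility Survey (Appendix 8), named to confirm where PrEP follow-up care is received, is an alcohol use disorder form with no PrEP item

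*Combined protocol and SAP*

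**What the plan says.** Section 10.5.2 (Treatment Facility Survey) gives Appendix 8 one task: "The treatment facility survey will be completed to confirm where the patient is receiving PrEP follow up care". For patients followed outside the Mount Sinai Health System, the same section adds that a signed release goes to the facility. Section 12.2 lists a facility follow-up questionnaire among the Aim 1 data sources.

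Other sections describe the wider confirmation step:

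- Section 9.5: "Assessment of engagement in PrEP care at 30, 60, and 90 days post enrollment will be verified by direct contact with the treatment provider/program", with record review as the route for patients linked inside the health system.
- Section 10.5.1 (Engagement in Treatment Survey): "participants will be asked to report PrEP use and engagement in PrEP care" at 30, 60 and 90 days, with the reported services then confirmed by the provider or the medical record.
- Section 9.3: "The medical release form is needed to confirm clinic follow-up for patients not receiving their follow-up care within the Mount Sinai Health System".

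Appendix 8 as printed has a date of assessment and five numbered items. Item 2 asks: "Was this patient engaged in a program at your facility or being treated at your office for their alcohol use disorder". After a yes, the respondent is told to "please review and answer the following questions". Item 4 reads: "Indicate the type(s) of treatment they are receiving for their alcohol use disorder".

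**The concern.** The text and the form disagree about what the form is for. Section 10.5.2 describes a PrEP follow-up form; Appendix 8 is a coherent instrument for another condition. The mismatch does not look like a typing slip or damage in conversion from PDF, because the question, the treatment options and the levels of care all fit together as an alcohol treatment survey.

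Two things are at stake. First, the trial takes its follow-up by telephone and its adherence data by self-report. Confirmation by provider or record is the only check on PrEP use and engagement in sections 9.5 and 10.5.1 that does not rest on the participant's word. For patients followed outside the health system, section 9.5 offers provider contact rather than record review. The one form named for facility confirmation should be able to hold a PrEP answer.

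Second, if the form is put to an outside clinic as worded, it suggests that the participant has an alcohol use disorder, a diagnosis the trial never assesses.

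**Working it through.** The plan gives no figure on this point, so the check compares the form's stated purpose with its content, item by item.

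| Appendix 8 item | What it records | Names PrEP or HIV? | Names alcohol use disorder? | Reached only after yes to item 2? |
|---|---|---|---|---|
| 1 | Provider type: office based, substance use program, inpatient, other | No | No | No |
| 2 | Whether the patient is engaged or treated | No | Yes | No (this is the gate) |
| 3 | Admission date or start of care | No | No | Yes |
| 4 | Treatment type: naltrexone (oral or injectable), detoxification, inpatient, other | No | Yes | Yes |
| 5 | Level of care, from none to medically managed inpatient, or other | No | No | Yes |

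Counts:

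- Items naming PrEP or HIV: 0 of 5.
- Items naming alcohol use disorder: 2 of 5 (items 2 and 4).
- Items behind the gate: 3 of 5 (items 3, 4 and 5).
- Items answered after a no at item 2: 5 − 3 = 2 (items 1 and 2).

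**Natural reading of item 2.** The alcohol phrase governs both halves of the question. A PrEP clinic that does not treat the patient for alcohol use disorder answers no and stops. The form then holds the assessment date, a provider type and the no. Item 3, the one item that could serve PrEP care unchanged, is closed off.

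**Looser reading.** A facility could take the first half of item 2 (engaged in a program there) as covering a PrEP program and answer yes. It could then give a start date at item 3, choose the other option at item 4, and choose outpatient at item 5. Item 4 still asks about alcohol treatment, and nothing on the form separates this yes from a yes that means alcohol treatment.

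On neither reading does a printed item record that the patient is in PrEP care. Nor does the form as printed have a field for the facility's name, so the question of where is reduced to a type of provider.

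**Is alcohol use disorder relevant elsewhere in the trial?** The eligibility criteria in section 8.2 have no alcohol criterion, and the outcomes in section 21.0 have no alcohol measure. Alcohol is mentioned in the sexual behavior questions (Appendix 4) and as an example of past history on the serious adverse event form (Appendix 10). Neither is a diagnosis of alcohol use disorder, and that term appears nowhere outside Appendix 8.

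**Is there another form?** The contents list names no other form for provider confirmation, and section 10.5.2 cites Appendix 8 specifically. The text of Appendix 9 (the release) was not available to check, and the contents list omits Appendix 10, so the list alone does not prove that no other form exists.

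**The case against.** The strongest case on the other side accepts the mismatch and disputes how far it reaches. Most of it stands.

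- **Primary outcome.** A reader might infer that the primary outcome cannot be verified. The documents do not support that. Section 10.5.2 gives Appendix 8 only the question of where care is received. PrEP use and engagement belong to a separately named survey in section 10.5.1, which starts from patient report and is confirmed by provider or record. Neither that section nor section 9.5 names Appendix 8. Direct contact, the signed release and record review all remain.
- **Power.** A reader might carry the defect into the sample size section, where the power table is built "with the assumption that those retained in care will be using PrEP". That is an illustrative planning assumption and does not depend on this form.
- **The skip at item 2.** It follows from the natural reading, not the only one. The looser reading would open items 3 to 5, so the count of 3 skipped items is conditional.
- **What outside clinics see.** Section 10.5.2 says that the release is sent; it does not say who completes the survey or how. The wording of the items is addressed to a provider, so the worry about implying an alcohol diagnosis is reasonable, but it depends on the form being used that way.
- **A wrong attachment.** Section 5.1 schedules operating procedures that cover data management and quality assurance, and the study data go into REDCap. The actual entry fields are not shown. The right fields may exist there and the wrong form may simply have been appended.

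None of this removes the contradiction. If the wrong file was appended, the protocol still names it, and staff who follow the protocol would use it.

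**Conclusion.** The point holds as an internal inconsistency: the form named to confirm where PrEP care is received is an alcohol use disorder form, and 0 of its 5 items mention PrEP or HIV. Used as written, it would record the wrong condition or, on the natural reading of item 2, little beyond a provider type and a no.

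It should be fixed, but it is not a threat to the trial's validity. Verification is still possible by the other routes. The documents do not say how many participants would be followed outside the health system, so the effect on results cannot be computed, and no bias or loss of power is claimed.

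The conclusion assumes that Appendix 8 as printed is complete (it ends cleanly at the last option of item 5) and that no PrEP version of the form exists elsewhere. The conflict in section 11.1.2 over whether retention in care is a primary or a secondary outcome is a separate matter and neither adds to nor takes from this point.

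**What to change.** Replace the alcohol use disorder content of Appendix 8 with PrEP items, with no alcohol question as a gate:

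1. Name of the facility or provider.
2. Whether the patient is in PrEP care there (yes or no).
3. Date PrEP care began, or date of the last PrEP visit.
4. Whether care is ongoing at the 30, 60 or 90 day contact.

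Items 1 and 2 meet the purpose in section 10.5.2. Items 3 and 4 go a little further, so that the form also serves the confirmation of engagement at each time point that sections 9.5 and 10.5.1 require. Keep all four within what the signed release covers; its text must be checked first. Collect the same items from record review for patients followed inside the health system, so that both sources classify engagement in the same way. State in section 10.5.2 who completes the form and how.

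The cost is one revised form, the same few fields for record review, and an IRB amendment. No extra contact with participants is needed. If a correct PrEP form is already in use, the fix reduces to attaching it in place of the printed one.

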Appendix 10: Adverse Event Reports

Adverse Event Report (AD1)

Adverse Event Onset Date:

Adverse Event Reference number:

Effective Date: 4/20/2021

End Date: 3/18/2022

1. Adverse event name:
2. Date site became aware of the event:
3. Severity of event (pick one):
 - a. Grade 1 – Mild
 - b. Grade 2 – Moderate
 - c. Grade 3 – Severe
4. Is there a reasonable possibility that study medication caused the event? Yes No
 - a. If “Yes”, action taken with study medication (select one):
 - i. None
 - ii. Decreased drug
 - iii. Increased drug
 - iv. Temporarily stopped drug
 - v. Permanently stopped drug
 - vi. Participant terminated from study
5. If not caused by the study medication, alternative etiology (select one):
 - a. None apparent
 - b. Study disease
 - c. Concomitant medication
 - d. Other pre-existing disease or condition
 - e. Accident, trauma, or external factors
 - f. Concurrent illness/condition (not pre-existing)
 - g. Study procedures
 - h. Other:
6. Outcome of event (select one):
 - a. Recovering/resolving (skip question 7)
 - b. Recovered/resolved
 - c. Recovered/resolved with sequelae
 - d. Not recovered/not resolved (skip question 7)
 - e. Fatal (skip question 7)
 - f. Unknown (skip question 7)
7. Date of resolution or medically stable:

A response of “Yes” to any of the following will designate this as a Serious Adverse Event (SAE). The Serious Adverse Event Summary (AD2) form should be completed for all Serious Adverse Events reported.

8. Was this event associated with:
If more than one option applies, select the most serious.
 - a. Is the adverse event associated with a congenital anomaly or birth defect?
 - b. Did the adverse event result in persistent or significant disability or incapacity?
 - c. Did the adverse event result in death?
 - i. If “Yes”, date of death:
 - d. Did the adverse event result in initial or prolonged hospitalization for the participant?
 - i. If “Yes”,
 1. Date of hospital admission:
 2. Date of hospital discharge:
 - e. Is the adverse event life threatening?
 - f. Is the adverse event an “Other serious” event (important medical event)?

Comments:

Study staff completing form:

Date completed:

Serious Adverse Event Summary (AD2)

Adverse event onset date:

Initial narrative description of serious adverse event:

1. Relevant past medical history: Yes No Unknown

Allergies, pregnancy, smoking and alcohol use, hypertension, diabetes, epilepsy, depression, etc.

Expand on relevant past medical history:

2. Medications at the time of event: Yes No Unknown

Be sure to assess for dosage and date of last dose for the study medication, and any prior/concomitant medications as needed.

Medication (Generic Name)	Indication

3. Treatments for the event: Yes No Unknown

Treatment	Indication	Date Treated (mm/dd/yyyy)

4. Labs/tests performed in conjunction with this event: Yes No Unknown

Lab/Test	Findings	Date of Test (mm/dd/yyyy)

5. Follow-up:

Include labs/test results as they became available, clinical changes, consultant diagnosis, etc.

Comments:

Study staff completing form:

Date completed:

Patient ID

Date

 / /
MM DD YYYY

Level

Week in
level

Please indicate all symptoms you have experienced in the past week. These symptoms may or may not have been caused by your treatment.

